- Group 2: secukinumab 150 mg (1mL) once every four weeks till (and including) Week 256. After approval and implementation of Amendment 1, patients may be escalated to 300 mg as judged appropriate by the investigator.

Study treatment dose adjustments are not permitted until Week 156.

Starting from Week 156 (i.e. during the open label study period), after approval and implementation of Amendment 1, the secukinumab dose should be escalated from 75 mg to 150 mg for patients whose signs and symptoms are not fully controlled with the current dose of 75 mg, and may improve with higher dose as judged by the investigator.

Further, the dose should also be escalated to 300 mg for patients currently on 75 mg or 150 mg, and whose signs and symptoms are not fully controlled and may improve further with an increase in dose as judged by the investigator.

Dose escalation from secukinumab 75 mg to 300 mg can be done either in one step or in two steps (first 150 mg, then 300 mg based on investigator's judgement).

For patients escalated to 150 mg or 300 mg, no dose reduction can be performed at a later stage.

Subjects will continue to be on background methotrexate (MTX) (if they were already taking MTX at the start of core study CAIN457F2306) throughout the study. The dose of MTX may be adjusted as deemed appropriate by the investigator.

In addition subjects will be allowed to start or adjust the dose of corticosteroids and non-steroidal anti-inflammatory drugs (NSAIDs) as deemed appropriate by the investigator.

[figure not shown]
Before enrolment in this extension study, all subjects electing to continue will sign an Informed Consent form. After approval and implementation of Amendment 1, all subjects electing to continue will sign a new version of the Informed Consent form. Detailed instructions for self-administration of the s.c injection using the PFS formulation will be provided to each subject. Each injection will be administered into an appropriate injection site of the body. For the first 6 months of the extension study (up to Week 128), all injections will be performed at site. Starting from Week 132 subjects will have the choice of self-administration at home or continuing with administration at site, based on personal preference and the investigator's clinical judgment. Site staff or caregiver (once trained) will administer the injection to subjects who are not able or feel insecure to self-administer the PFS injection.

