5.5.5 Permitted dose adjustments and interruptions of study treatment

Study treatment dose adjustments are not permitted until Week 156.

After approval and implementation of Amendment 1, patients previously treated with secukinumab 75 mg may receive either 75 mg, 150 mg or 300 mg, and patients previously treated with secukinumab 150 mg may receive 150 mg or 300 mg, as deemed appropriate by the investigators. The decision may be taken at any on-site visit. When dose escalation has been performed for one patient, no dose reduction can be performed at a later stage.

Study treatment interruption is also not permitted with the following exceptions:

- Study treatment interruption is permitted only if, in the opinion of the investigator, a subject is deemed to be placed at a significant safety risk unless dosing is temporarily interrupted. In such cases study treatment should be interrupted only during the time that this risk is present and ongoing. Study treatment can be restarted at the next scheduled visit after resolution of the safety risk.
- The effect of secukinumab on live vaccines is unknown; therefore live vaccines should not be administered during participation in the study. In case a live vaccine has been

administered due to a medical urgency, study treatment should be interrupted for 12 weeks.

The reason for any study treatment interruption must be recorded on the corresponding eCRF page.

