5.1 Treatment groups

The arms included in efficacy tables are based on the treatment sequence (picturing also the up-titration) for the periods up to the final lock at week 260. Two separate columns will display the assigned and actual treatment resulting in the following treatment sequences:

Efficacy:

- AIN457 10 mg/kg - 75 mg
- AIN457 10 mg/kg - 75 mg - 150 mg
- AIN457 10 mg/kg - 75 mg - 300 mg
- AIN457 10 mg/kg - 150 mg
- Placebo - AIN457 75 mg
- Placebo - AIN457 75 mg - 150 mg
- Placebo - AIN457 75 mg - 300 mg
- Placebo - AIN457 150 mg

After week 52 the combination of assigned treatment will also be shown.

- AIN457 75 mg & Placebo - AIN457 75 mg
- AIN457 150 mg & Placebo - AIN457 150 mg

The treatment sequence following up-titration for the combined groups will be:

- AIN457 75 mg & Placebo - AIN457 75 mg - 150 mg
- AIN457 75 mg & Placebo - AIN457 75 mg - 300 mg
- AIN457 150 mg & Placebo - AIN457 150 mg – 300 mg

Cases might up-titrate twice; for these cases the treatment prior to each up-titration will be displayed (that is not the assigned treatment for the 2nd observed up-titration). Therefore, at the graphical representation of up-titration the actual treatment dose prior to the switch will be displayed.

Regarding safety, the arms included in the entire treatment period are as follows.

- Any AIN457 75 mg
- Any AIN457 150 mg
- Any AIN457 300 mg
- Any AIN457 (if appropriate)

Placebo group will be included at the in-text tables and listings of the CSR.

In the safety listings the groups will be the following:

- AIN457 10 mg/kg - 75 mg
- AIN457 10 mg/kg - 150 mg
- Placebo AIN457 75 mg
- Placebo AIN457 150 mg
- Placebo not re-randomized.

6 Subgroup definitions

The primary endpoint and secondary endpoints will be evaluated for TNF-alpha inhibitor status and by concomitant MTX use (ACR20/50, [REDACTED]).

7 Assessment windows, baseline and post baseline definitions, missing data handling

Baseline and post-baseline definitions

In general, a *baseline* value refers to the core study and is the last measurement made prior to administration of the first dose of study treatment in core. Baseline information will be presented appropriately in the “by visit” summaries in both safety and efficacy tables.

A post-baseline value refers to a measurement taken after the first dose of study treatment in core study.

Analysis visit windows

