12.4 Analysis of Primary Variable(s)

The primary efficacy variable(s) is the clinical response to treatment according to ACR20, ACR50 and ACR 70 improvement in disease activity over time up to Week 260.

ACR response criteria denote the response (i.e., improvement) in signs & symptoms of the disease of a subject compared to baseline of the core study.

The analysis of the primary variables will be based on the FAS. Primarily, CRP will be used instead of ESR to calculate ACR response; ESR will only be used in the event CRP is missing.

Shift tables will be provided comparing the subject's ACR evaluation at the pre up-titration visit relative to the observed data of the following week intervals after up-titration: (12-32 weeks), (36-56 weeks) and (60-80 weeks). The ACR grouping presented in the table will be: $ACR < 20$, $20 \leq ACR < 50$, $50 \leq ACR < 70$, $ACR \geq 70$.

Graphical representation (line plots) of ACR20, ACR50 and ACR70 response over time and Sankey-style bar chart for the ACR response within the subjects that up-titrated from 150 mg to 300 mg (provided that up-titration has been occurred for more than 8 weeks) will be drawn from the observed data.

Additionally, observed data tables will summarize the ACR20, ACR50 and ACR70 response following up-titration when assessed. Results will be illustrated in line plots.

Also individual subject listings of the ACR components as well as for the ACR20/50/70 response will be given.

Statistical model, hypothesis, and method of analysis

No formal hypotheses are planned for this study. The proportion of subjects meeting the ACR criteria (ACR20, ACR50, and ACR70) will be descriptively summarized for each treatment by absolute and relative frequencies followed by 95% confidence intervals for the proportion of patients responding to treatment according to the ACR criteria from Week 1 onwards based on the pooled data from core and extension study. Results regarding ACR20/50/70, will be presented overall in the FAS population as well as in subgroups by TNF α status (naive or IR) and by concomitant use of MTX as appropriately.

Placebo group (core study) in efficacy analysis will not be considered.

All the above efficacy variables will be analyzed on the FAS (unless otherwise specified) for all applicable analysis visits based on the observed data.

For binary variables, the proportion of responders along with the 95% CI will be presented by treatment groups over analysis visits.

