No visit windows were used in case of up-titrations. The before up-titration measurement is considered as the last visit measurement, performed on or before the date that patient took the up-titration dose. The up-titration data analysis will be based on week intervals; it is accounting for the time period between the actual date of exposure to the up-titrated dose and the last visit date of the subject:

- 4 – 8 weeks after up-titration
- 12 – 32 weeks after up-titration
- 36 – 56 weeks after up-titration
- 60 – 80 weeks after up-titration
- 84 – 104 weeks after up-titration

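### The SAP does not end the post-up-titration period at a second up-titration and has no 75-150-300 mg sequence, so ACR values measured on 300 mg can be attributed to the 75-to-150 mg step

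*SAP*

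**What the plan says.** Protocol 3.1 provides for the two-step path: "Dose escalation from secukinumab 75 mg to 300 mg can be done either in one step or in two steps". Protocol 5.5.5 sets the timing: "The decision may be taken at any on-site visit". No dose change is allowed before Week 156, and none until Amendment 1 is in force.

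SAP 5.1 foresees the case: "Cases might up-titrate twice; for these cases the treatment prior to each up-titration will be displayed". For the graphs it adds that "at the graphical representation of up-titration the actual treatment dose prior to the switch will be displayed". For the efficacy tables, "Two separate columns will display the assigned and actual treatment resulting in the following treatment sequences". For the combined groups the up-titration sequences listed are 75-150, 75-300 and 150-300 mg; 75-150-300 mg is not among them.

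SAP 17.1 uses no visit windows for up-titration data. The pre-up-titration value is the last one on or before the date of the new dose. Later values are placed in intervals of 4-8, 12-32, 36-56, 60-80 and 84-104 weeks, based on "the time period between the actual date of exposure to the up-titrated dose and the last visit date of the subject".

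SAP 12.4 uses three of these intervals (12-32, 36-56 and 60-80 weeks): "Shift tables will be provided comparing the subject's ACR evaluation at the pre up-titration visit relative to the observed data". It also plans tables and line plots of ACR20/50/70 response after up-titration.

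For safety, SAP 14 counts a subject whose dose escalates in both dose groups, separated by the start and stop dates of each exposure. No matching sentence exists for efficacy.

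**The concern.** The up-titration tables and plots are there to show what follows each escalation step. For a subject who goes from 75 to 150 and later to 300 mg, the first step's interval clock keeps running after 300 mg has begun. A late value in the 75-to-150 mg summary may therefore have been measured on 300 mg, and the same value belongs to the 150-to-300 mg summary as well. The two step-specific summaries would then share observations.

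The subjects concerned are not a random subset. Under Protocol 3.1 the second step is for those whose signs and symptoms are not fully controlled on the current dose. With multiple imputation and MMRM dropped because of up-titration (SAP 2 and 12.3), these observed-data summaries carry much of the description of escalation, so a reader should be able to tell which dose each value reflects.

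**Working it through.** The plan states no figure on this point, so there is none to reproduce. The check places the scheduled ACR visits in the SAP intervals, counted from each escalation.

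**Inputs**
- Scheduled on-site visits at which a dose can be raised (Protocol Tables 6-1 to 6-3): Weeks 156, 168, 180, 192, 208, 220, 232, 244. Ordered pairs of first and second step: 8 × 7 / 2 = 28.
- Later visits with the ACR components (Tables 6-2 and 6-3): Weeks 180, 208, 232, 260.
- Intervals: the five in SAP 17.1.
- Assumptions: the new dose starts at the decision visit; a value taken at that visit is pre-dose (Protocol 5.5.4 puts assessments before dosing); visits are on schedule. Optional 4-weekly site visits by subjects who do not self-inject, and unscheduled visits, are left out.

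**One example:** 150 mg from Week 156, 300 mg from Week 180.

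| ACR visit | Weeks after step 1 | Interval | Weeks after step 2 | Interval | Dose at measurement |
|---|---|---|---|---|---|
| 180 | 24 | 12-32 | pre-dose | – | 150 mg |
| 208 | 52 | 36-56 | 28 | 12-32 | 300 mg |
| 232 | 76 | 60-80 | 52 | 36-56 | 300 mg |
| 260 | 104 | 84-104 | 80 | 60-80 | 300 mg |

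**All 28 pairs.** Each ACR visit after the first step is placed in an interval counted from that step. It overlaps if it also comes after the second step and falls in an interval counted from there.

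| Interval after step 1 | Placements | Measured on 300 mg and also placed after step 2 | Measured on 150 mg |
|---|---|---|---|
| 12-32 weeks | 28 | 4 | 24 |
| 36-56 weeks | 27 | 15 | 12 |
| 60-80 weeks | 22 | 18 | 4 |
| 84-104 weeks | 13 | 13 | 0 |
| Total | 90 | 50 | 40 |

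Every pair has at least one overlap. Week 260 alone shows this: it lies 104, 92, 80, 68, 52, 40, 28 or 16 weeks after the eight possible escalation visits, and each of these falls in a listed interval. In the three intervals of the ACR shift tables, the overlap is 4 + 15 + 18 = 37 of 28 + 27 + 22 = 77 placements.

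At 12-32 weeks an overlap arises only when the second step comes at the very next scheduled on-site visit, and then only for Weeks 156-168, 180-192, 208-220 and 232-244.

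These counts give each possible schedule equal weight. They show where the overlap falls, not how many patients are involved.

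**The case against.** **The grouping is undefined.** The SAP nowhere says that values on 300 mg are reported as response to 150 mg. It plans an actual-treatment column and does not say whether a two-step subject sits under 75-150, sits under 75-300 or moves between them. This stands, and a reader who infers a proven bias in favour of 150 mg goes beyond the text. It does not close the gap: under a 75-300 grouping, values on 150 mg would be shown under 300 mg, and an actual-treatment column that changed over time would still leave the interval rule as it is.

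**The sentence in SAP 17.1 may only explain how elapsed time is measured.** That is possible. Even so, no sentence stops the clock at a second step.

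**The outputs are descriptive.** There are no formal hypotheses, and any intervals or p-values are exploratory. The sequence tables, the Sankey-style chart for 150 to 300 mg, the HAQ-DI figures after up-titration and the individual listings also bear on escalation, so the ACR intervals are not the only source. This stands and limits the consequence.

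**Following subjects from the first escalation whatever happens later is a legitimate description.** It is, if labelled so. The SAP does not label it so, and it treats each step as a separate up-titration.

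**Conclusion.** The gap is real. SAP 17.1 does not end the first period at a second up-titration, and SAP 5.1 provides no group for 75-150-300 mg, although the SAP expects such subjects. On the literal text, ACR values measured on 300 mg can be attributed to the 75-to-150 mg step and also appear in the 150-to-300 mg summary. This falls mainly in the 36-56 week and later intervals and little at 12-32 weeks.

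Two stronger readings are not supported:
- A reader might infer that subjects are counted twice. The same value can appear in two separate summaries, but not twice in one proportion. By-visit results by assigned dose are not affected.
- A reader might try to size the distortion. Taking 10-40% of 75-to-150 mg escalators as going on to a second step, and 15-40% of those reaching ACR50 on 300 mg, the product runs from 0.10 × 0.15 = 1.5 to 0.40 × 0.40 = 16 percentage points. The share has no source in the documents. The product also requires every second-step subject to have been an ACR50 non-responder on 150 mg, whereas escalation rests on investigator judgement and Amendment 1 also argues for 300 mg on skin response. And it requires every value in the interval to have been taken on 300 mg. Neither the size nor the direction can be stated from the documents.

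**What to change.** - SAP 17.1: end the follow-up of an up-titration at the earlier of the subject's last visit and the first dose of the next up-titration. This matches the start-and-stop rule that SAP 14 already applies to safety.
- SAP 5.1: add a 75-150-300 mg sequence and its combined version, and state where a two-step subject's values sit before and after the second step.
- SAP 12.4: for each interval, report how many subjects left the 75-to-150 mg summary because they escalated again, so that the loss of subjects not controlled on 150 mg is visible. A shift-table category 'escalated again' is one way to do this.

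The cost is a few lines of text and one date condition. Protocol 5.5.4 already requires dose changes to be recorded on the Dosage Administration Record eCRF. The downside is one more small column and fewer subjects in the later 75-to-150 mg intervals: in the enumeration 24 of 28, 12 of 27, 4 of 22 and 0 of 13 placements remain. Those who remain are increasingly subjects who stayed on 150 mg, which is why the count of further escalations must be shown beside them.

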17.2 Interim Locks dates

Annual locks for analysis purposes were performed.

This the final lock of the study at week 260. It includes all subjects who have completed week 260 assessment and/or the follow up treatment visit.

17.3 Statistical methodology and assumptions

17.3.1 Analysis of continuous data

17.3.1.1 Summary statistics for continuous data

Summary statistics (including N, mean, standard deviation, minimum, lower quartile, median, upper quartile, maximum) will be provided for continuous data by visit and treatment group.

17.3.2 Analysis of binary (and categorical) data

17.3.2.1 Summary statistics for binary and categorical data

Summary statistics for discrete variables will be presented in contingency tables and will include count and frequency in each category. If applicable, confidence intervals will be derived as well based on the score method including continuity correction [Newcombe (1998)]:

With z as (1-alpha/2)-quantile of the standard normal distribution (SAS: $z=PROBIT(1-alpha/2)$), n as total number of subjects (i.e. number of subjects in the denominator), and p as estimated crude incidence (number of subjects with event / n) it is $q=1-p$

Then the lower limit is

$$L = 100 \times \max \left(0, \frac{2np + z^2 - 1 - z \sqrt{z^2 - 2 - \frac{1}{n} + 4p(nq+1)}}{2(n+z^2)} \right)$$

and the upper limit is

$$U = 100 \times \min \left(1, \frac{2np + z^2 + 1 + z \sqrt{z^2 + 2 - \frac{1}{n} + 4p(nq-1)}}{2(n+z^2)} \right)$$

SAS code for risk difference:

```
Proc freq data=acr order=formatted;
```

```
Tables response*trt/ riskdiff;
```

```
Run;
```

(Note the response value should be sorted with '1' ahead of '0'.)

17.3.3 Crude incidence and related risk estimates

17.3.3.1 Crude incidence and 100*(1-α)% confidence interval

For n subjects, each at risk to experience a certain event with probability π , the crude incidence is estimated as $p=x/n$, where x is the number of subjects with the event.

Absolute and relative frequencies will be displayed as well as 95% confidence interval for the relative frequency based on the score method including continuity correction (Newcombe 1998).

With z as $(1-\alpha/2)$ -quantile of the standard normal distribution (SAS: $z=PROBIT(1-\alpha/2)$), n as total number of subjects (i.e. number of subjects in the denominator), and p as estimated crude incidence (number of subjects with event / n) it is $q = 1 - p$.

Then the lower limit is:

$$L = \max \left(0, \frac{2np + z^2 - 1 - z\sqrt{z^2 - 2 - \frac{1}{n} + 4p(nq + 1)}}{2(n + z^2)} \right)$$

and the upper limit is

$$U = \min \left(1, \frac{2np + z^2 + 1 + z\sqrt{z^2 + 2 - \frac{1}{n} + 4p(nq - 1)}}{2(n + z^2)} \right).$$

Note: if $L > (100 \times p)$ then $L = (100 \times p)$ and if $U < (100 \times p)$ then $U = (100 \times p)$.

If appropriate, an exact 100*(1-α)% confidence interval (Clopper-Pearson 1934) will be obtained by using the SAS procedure PROC FREQ with the EXACT BINOMIAL statement. However, the confidence interval derived via the score method including continuity correction will be the default in safety analyses.

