- PASI75 response rates at Week 24 were 63.4%, 48.3%, 28% and 16.3% with 300mg, 150mg, 75mg and placebo respectively.
- PASI90 response rates at Week 24 were 48.8%, 32.8%, 12% and 9.3% with 300mg, 150mg, 75mg and placebo respectively.
- DAS-28 CRP mean change from baseline at Week 24 was -1.61, -1.58, -1.12 and -0.96 with 300mg, 150mg, 75mg and placebo respectively.
- SF36-PCS mean change from baseline at Week 24 was 7.25, 6.39, 4.38 and 1.95 with 300mg, 150mg, 75mg and placebo respectively.

This trend from CAIN457F2312 is reflected in the week 104 results of CAIN457F2306, indicating that in the present longer term efficacy extension study, a higher dose could be more beneficial to patients. Secukinumab 150mg had clinically superior ACR50 and PASI75/90 response rates compared to 75mg at Week 104:

- ACR50 response rates at Week 104 were 46.4 % and 35.5% with 150mg and 75mg respectively.
- PASI75 response rates at Week 104 were 82.9 % and 70.2% with 150mg and 75mg respectively.
- PASI90 response rates at Week 104 were 69.5 % and 50.0% with 150mg and 75mg respectively.

As a conclusion, there is strong evidence that the 75 mg dose administered every 4 weeks in PsA patients provides insufficient exposure to achieve optimal, clinically relevant improvements in all subgroups and across multiple domains in this debilitating multifaceted chronic disease.

300 mg sc dose of secukinumab offers increased benefit for TNF α -inadequate responder patients and in patients with moderate to severe plaque psoriasis:

While secukinumab 150 mg sc and 300 mg sc regimens are both more efficacious than placebo regardless of TNF α inhibitor status, the 300 mg sc regimen provided the greatest efficacy across multiple PsA domains including ACR20, ACR50, ACR70, HAQ-DI, PASI 75, PASI 90, SF-36 PCS, and presence of dactylitis and enthesitis in TNF-IR patients.

Evidence of dose response was shown in TNF-IR patients favoring secukinumab 300 mg sc over 150 mg sc at the Week 24 efficacy endpoint used for the primary and secondary efficacy analyses of CAIN457F2312, while the 75 mg sc dose showed overall lower efficacy. Indeed, ACR20/50/70 response rates at Week 24 in TNF-IR patients were higher with secukinumab

300 mg sc compared to 150 mg sc (45.5% vs 29.7%, 27.3% vs 18.9% and 15.2% vs 10.8% respectively), while 75 mg sc failed to differentiate from placebo in all ACR endpoints. This trend was maintained up to week 52.

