14.1 Adverse events

The crude incidence of treatment emergent adverse events on secukinumab (i.e. events started after the first dose of secukinumab in core study or events present prior to the first dose of secukinumab but increased in severity based on preferred term and within 84 days after last dose of secukinumab) will be summarized by primary system organ class and preferred term for the entire treatment period. Confidence intervals for the crude rate will be derived as described in Section 17.2.3.1 In addition, exposure time-adjusted rates (incidence rate) including 95% confidence intervals will be provided for selected terms for the entire treatment period, (see Section 17.2.4.1) to adjust for differences in exposure.

Adverse events reported will be presented in descending frequency according to its incidence in total secukinumab group (combining all secukinumab treatment groups) starting from the most common event.

Summary statistics will be provided by primary system organ class and preferred term for the entire treatment period for all TEAEs, for serious TEAEs, for possibly related TEAEs, for deaths, for TEAEs causing treatment discontinuation, other serious or clinically significant treatment emergent adverse events or related discontinuations, for TEAEs leading to temporary dose interruptions, for SPP risks and for adjudicated major adverse cardiovascular events (MACE). Separate summaries for adverse events suspected to be related to study drug, will also not be displayed in the current analysis.

TEAEs will also be summarized by primary system organ class and preferred term for the entire treatment period in time segments of 52 and 26 weeks.

Summaries (crude incidence only) will be presented for TEAEs by maximum severity as well. If a particular AE 'severity' is missing, this variable will be listed as missing and treated as missing in summaries.

If a subject reported more than one adverse event with the same preferred term, the adverse event with the greatest severity will be presented. If a subject reported more than one adverse event within the same primary system organ class, the subject will be counted only once with the greatest severity at the system organ class level, where applicable.

When adjudication is required of major cardiovascular events, a summary of those types of events as reported by the investigator and confirmed by adjudication will be provided.

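### The score-interval rule gives wrong limits as written: SAP 17.3.3.1 mixes proportions with percentages, 17.3.2.1 omits the boundary correction, and SAP 14.1 points to sections that do not exist

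*SAP*

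**What the plan says.** SAP 17.3.3.1 defines the crude incidence as p = x/n and calls for a "95% confidence interval for the relative frequency based on the score method including continuity correction". The printed limits are L = max(0, ...) and U = min(1, ...), with no factor 100. A note below them resets L to 100 × p if L is above 100 × p, and for the upper limit reads "if $U < (100 \times p)$ then $U = (100 \times p". The section allows an exact Clopper-Pearson interval where appropriate, but adds that "the confidence interval derived via the score method including continuity correction will be the default in safety analyses".

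SAP 17.3.2.1 covers binary and categorical data. It says "confidence intervals will be derived as well based on the score method including continuity correction" and prints the same two limits multiplied by 100. No boundary note follows.

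These rules serve two sets of results:

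- **Primary efficacy.** SAP 12.4 plans "95% confidence intervals for the proportion of patients responding to treatment according to the ACR criteria from Week 1 onwards", by treatment and by TNF and MTX subgroup. Protocol 9.4.2 makes this interval the means of evaluating efficacy.
- **Safety.** SAP 14.1 says "Confidence intervals for the crude rate will be derived as described in Section 17.2.3.1" and refers to Section 17.2.4.1 for exposure-adjusted rates. The heading at that number is "17.2 Interim Locks dates", and it has no subsections. The rules stand at 17.3.3.1 and 17.3.4.1.

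**The concern.** The note is needed because this closed form does not return 0 as the lower limit at 0/n, or 1 as the upper limit at n/n. It has to be on the same scale as the limits and to accompany the formula wherever that is used. Neither section meets both conditions: 17.3.3.1 has the note on the wrong scale, and 17.3.2.1 has the right scale and no note.

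The two faults differ in how easily they would be noticed. A safety table with limits on two scales looks wrong at once. An efficacy row showing 0% response with an interval that starts at 0.9% looks plausible and could pass checking. Such rows can arise because SAP 5.1 splits efficacy into eight treatment sequences plus combined and up-titrated groups, and SAP 12.4 adds subgroups and visits from Week 1.

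The study has no formal hypotheses, so the intervals are its main expression of precision.

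**Working it through.** The SAP prints no numerical interval to reproduce, so the check applies its formulas as written.

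**Inputs.** Two-sided 95%, so z = 1.95996 and z² = 3.84146; p = x/n and q = 1 − p. The event counts below are hypothetical. The denominators 460 (extension enrolment, Protocol section 4) and 606 (core enrolment, Protocol 1.1 and 1.2) only set a realistic size. They are not the denominators of the safety columns.

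**Formulas, as proportions.**

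- L = [2np + z² − 1 − z√(z² − 2 − 1/n + 4p(nq + 1))] / [2(n + z²)]
- U = [2np + z² + 1 + z√(z² + 2 − 1/n + 4p(nq − 1))] / [2(n + z²)]

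At interior counts these agree to five decimals with a direct solution of |p − θ| − 1/(2n) = z√(θ(1 − θ)/n). For example, 81/263 gives 0.25351 to 0.36818 both ways. The score formula itself is right.

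**1. The note in 17.3.3.1.** For 20/460, p = 0.04348, 100p = 4.348 and the denominator is 927.683.

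- L = (40 + 3.84146 − 1 − 17.36919)/927.683 = 0.02746
- U = (40 + 3.84146 + 1 + 17.76847)/927.683 = 0.06749
- Since 0.06749 < 4.348, the note sets U = 4.348. L is not above 4.348, so it stays 0.02746.

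| Count | Literal 17.3.3.1 | Both on the percent scale |
|---|---|---|
| 20/460 | 0.0275 to 4.35 | 2.75% to 6.75% |
| 5/606 | 0.0030 to 0.83 | 0.30% to 2.03% |
| 1/606 | U = 0.165 | U = 1.06% |
| 0/460 | 0 to 0.0103 | 0% to 1.03% |

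This is general. Over all n from 1 to 606 and x ≥ 1, U is at most about 6.5 times p, so it is always below 100p. The note overwrites U in all 183,921 such pairs. At x = 0 the lower reset works, because 100p and p are both 0.

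**2. No note in 17.3.2.1.** At x = 0 the lower limit reduces to [z² − 1 − z√(z² − 2 − 1/n)] / [2(n + z²)].

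- For n = 10: (2.84146 − 2.58645)/27.683 = 0.0092, that is 0.92%, although the observed proportion is 0%.
- At n/n the upper limit is 100% minus the same amount: 10/10 gives 99.08%.

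| n | L at 0/n | U at n/n |
|---|---|---|
| 5 | 1.87% | 98.13% |
| 10 | 0.92% | 99.08% |
| 20 | 0.46% | 99.54% |
| 50 | 0.18% | 99.82% |
| 100 | 0.09% | 99.91% |
| 460 | 0.02% | 99.98% |

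The estimate is excluded at every 0/n and n/n for n from 1 to 606, which is 2 × 606 = 1,212 pairs. It is excluded at none of the 183,315 interior pairs.

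**3. How often a 0/n cell might occur.** The documents give no cell sizes, so n is an assumption and only a range can be shown. The chance of no responders is (1 − p)^n.

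- A low response rate is the Week 24 ACR70 figure of 10.8% for TNF-IR patients on 150 mg in the companion study (Protocol, Amendment 1 rationale: "27.3% vs 18.9% and 15.2% vs 10.8% respectively", ACR50 then ACR70, 300 mg versus 150 mg). The chance is 56% at n = 5, 32% at n = 10, 10% at n = 20 and 0.3% at n = 50.
- At the core study's own Week 104 ACR50 rates in the same rationale (35.5% on 75 mg, 46.4% on 150 mg), the chance at n = 10 is 0.645^10 = 1.2% and 0.536^10 = 0.2%.

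**The case against.** The best defence is that nobody would program 17.3.3.1 literally. The two sections print the same formula from the same source, one with the factor 100, and the note is itself in percent. Read together they allow one sensible meaning, and an upper limit equal to the estimate would fail any check. This largely stands for the safety rule. A factor lost when the PDF was read cannot be wholly excluded, but it is unlikely because the factor survives in 17.3.2.1.

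The defence does not reach 17.3.2.1, where the output looks reasonable. There the reply is that the effect is tiny: 0.09 percentage points at n = 100, 0.46 at n = 20, and nothing visible to one decimal at n = 460. The opposite limit, which carries the information (20.0% for 0/20), is unaffected. That is true, and it limits the weight of the point. It does not make an interval that excludes its own estimate correct.

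The 10.8% rate comes from another study at Week 24, whereas this extension enrols completers judged to benefit. That is why the range above includes the much lower chances at this programme's Week 104 ACR50 rates. ACR70 rates would be lower than ACR50 rates, and early visits could give zeros, so neither end settles the frequency.

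Finally, SAP section 4 treats the intervals as exploratory, and the wrong section numbers are clerical. Both are fair. The optional Clopper-Pearson interval does not repair the rule, because the score interval is the stated default.

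**Conclusion.** The concern holds, as a minor specification error. Followed as written, 17.3.3.1 gives an unusable upper limit for every non-zero event count, and 17.3.2.1 gives an interval that misses the estimate at 0/n and n/n only. The efficacy error is 1.87 percentage points at n = 5, 0.92 at n = 10 and under 0.1 at n = 100. How many table cells it touches is unknown.

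The exact Poisson intervals for exposure-adjusted rates in 17.3.4.1 are not affected, and no test or decision rule depends on the affected limits. Because the intended scale can be inferred, this is no evidence that any reported interval is wrong. The dead references in SAP 14.1 are confirmed but would not merit a comment alone.

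**What to change.** - In SAP 17.3.3.1, multiply L and U by 100, as 17.3.2.1 already does.
- State the same note in both sections: if L > 100p then L = 100p; if U < 100p then U = 100p. This gives L = 0 at 0/n and U = 100 at n/n.
- In SAP 14.1, change the references from 17.2.3.1 and 17.2.4.1 to 17.3.3.1 and 17.3.4.1.
- Check the interval macro at 0/n, n/n and one interior count. Correct results include 0/20: 0% to 20.05%; 20/20: 79.95% to 100%; 10/100: 5.16% to 18.04%.

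The cost is a few lines of SAP text and one short program check. No design element, data collection or analysis set changes.
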